Many of the symptoms of Long COVID have been targeted in other conditions using self-management interventions. For example, a non-condition specific self-management intervention know as the Chronic Disease Self-Management Program, shown excellent evidence of improving health status, including pain, shortness of breath, fatigue, illness intrusiveness, health distress and self-reported health when delivered online to people with chronic diseases of heart or lung, and type 2 diabetes [4]; and improved health distress, activity limitation, self-reported global health, and pain for participants with fibromyalgia and / or arthritis [5]. Generic self-management interventions may be of benefit to people living with any long-term impact of COVID-19.

Peer-delivery may be key. Many people with Long COVID describe feeling unsure of themselves, stigmatised by others, and disbelieved by health care professionals [6, 7]. Peer-delivered interventions offer validation and can provide knowledge and practical symptom management techniques, alongside reduced isolation[8]. Digital interventions must be carefully reviewed to ensure they do not deepen health inequalities, however are vital for people with fatigue (which reduce ability to engage with face-to-face meetings and travel) and with likely repeated restrictions on face-to-face meetings owing to the pandemic[2, 6, 9]. Effective peer-delivered self-management interventions use structured, empirically and theoretically grounded interventions, to supplement the social support provided by peer-led support. The use of trained peers offers a potentially cost-effective approach to supporting the needs of people with Long COVID [10]. Using trained peerfacilitators to deliver self-management interventions can address the sense of isolation and being disbelieved/ not understood that many people with long-term conditions experience [11].

Reviewing the literature, there are very few studies reporting outcomes of interventions to support people with Long COVID. Findings are being reported from studies offering physical exercise to people at various periods following acute COVID, including those who have experienced fatigue after COVID [12]. However, these are narrow in focus and do not provide broad intervention for managing the challenges of Long COVID. A case study of the use of cognitive-behavioural therapy to specifically address anxiety and depression has been published, providing an illustration of the use of this approach [13].

There has been no research to date to evaluate the impact of Long COVID peer-support, nor to evaluate a structured peer-delivered intervention. There is ongoing research seeking to understand what techniques for self-management people with Long COVID use [14]. The challenge that these interventions potentially place some "burden" on the person to remember and direct their own care, learning and using strategies with support has been acknowledged, as particular pertinent to people with Long COVID, many of whom experience fatigue and brain fog [15]. Nevertheless, self-management interventions are recommended in various clinical guidelines [15, 16]. The only published study of outcomes of rehabilitation interventions with a self-management element we could locate reported pre-post data from an intervention ran in routine clinical practice within the National Health Service in England [17]. This seven week "course" provides management advice for various symptoms, including emotional wellbeing. Significant improvements were found in health-related quality of life. This intervention is delivered "live" online by an interdisciplinary clinical team. Digital interventions that people can use "as and when" might be particularly important for Long COVID, owing to the high levels of fatigue and "brain fog".

Whilst there are funded studies underway to develop interventions [18], Long COVID clinics up and down the UK are faced with patients requiring support and treatment. As such, it is important to rapidly develop and evaluate interventions and support packages. There is then an outstanding need for an evidence-based, digitally delivered, peer-support self-management intervention for people living with Long COVID. Our research will evaluate a digital, peer-facilitated self-management intervention for adults with Long COVID symptoms. Our intervention has been developed from our existing self-management programme "Hope Programme for people living with cancer, in its digital format, using co-design methods with people with Long COVID [19]. We have conducted a simple

pre-post study of our intervention (in review, available in pre-print), which found a retention rate of 60% and provided initial support for the impact of the intervention through paired comparisons on positive wellbeing and self-efficacy to manage the long term condition [19]. Given the lack of established usual care or another effective intervention, there is no clear rationale for any active comparison group. Wait-list comparison was chosen for pragmatic reasons, as this study is embedded in existing planned provision of the Hope Programme

Objectives

The study seeks to test the following hypotheses: using a non-randomised wait-list control group, there will be improvements in positive mental wellbeing (primary outcome), self-efficacy, fatigue, depression, anxiety and loneliness following an 8-week digital peer-supported self-management intervention, for people living with long COVID.

Trial Design

This study is a pragmatic non-blinded non-randomised wait-list controlled pre-post study. The non-randomisation is partly for practical and ethical purposes. The study relates to an intervention that is already on offer to people in the Coventry Warwickshire and Rugby (CWR) area, owing to the way in which the service is funded. The Live well with HOPE project aims to reduce the negative impact of COVID-19 by empowering people across CWR to self-manage their health and wellbeing, develop social connections and peer-support opportunities. https://www.hopecwr.h4c.org.uk/ [The uptake of the intervention is predicted to be high, owing to its novelty and the high needs amongst people living with Long COVID. Given this, the wait-list control design will not alter people's access to the service. Randomisation to intervention or control group will not be conducted, rather people will be allocated to the intervention until full and the following participants will be allocated to the wait-list, as would occur if the study were not taking place.

Methods: Participants, interventions and outcomes Study setting

This study will take place in a community setting. Participants from the community will be able to access the intervention. The digital intervention delivery means they will be able to use this at their convenience. All data are collected online. Recruitment is not through any specific "site", rather via advertising. The funding prioritises courses for people living in the local community (Coventry, Warwickshire and Rugby), but the courses will be open to people from across the UK. Residents of Coventry, Warwickshire and Rugby will be given priority access to the Hope Programme.

Eligibility

Participants will be eligible if they are aged 18 years or older and self-defining as living with Long COVID. No eligibility checks will be conducted – self-report will be taken as evidence of person living with Long COVID. Participants must be fluent in English and have access to the necessary technology to take part in the digital intervention.

Interventions

Intervention group: Participants will receive the Hope Programme for Long COVID intervention This intervention was delivered entirely online with new content released each week. The web-based platform has information in written and audio/video formats and interactive exercises (e.g. quizzes, activities to record goals). There is the option to post comments and comment on other's posts. There is a digital social forum area where people can "chat" to one another. This provides significant

opportunity for peer support. The intervention is delivered by clinical exercise specialists from Atrium Health Atrium Health (www.atrium-health.co.uk), a Coventry-based social enterprise providing rehabilitation services.

The content includes an emphasis on pacing, as per guidelines for Long COVID [20]. The intervention can be accessed at the participants' convenience, for as many minutes and on as many occasions as desired. The content is summarised in Table 1.

Table 1: Weekly topics and activities

Session	Core content, in addition to weekly goal setting
Week 1:	Welcome and introductions
Introduction: Instilling hope	The benefits of positive emotions
	The power of gratitude
	Self-compassion
	Personalised goal setting
	Video: how to set achievable goals
	Dates for live sessions
Week 2:	Fatigue management; including the boom and bust cycle;
Long COVID Symptoms	prioritizing, planning, and pacing
	What is brain fog, and what can we do to help ourselves?
	 Forum topics: sharing experiences of managing fatigue and brain fog
	Further resources and links to Long COVID information and
	support
Week 3:	Coping with unhelpful thinking patterns
Managing stress	Understanding and managing stress
	Self-compassion and acceptance
	Mindfulness for stress management and meditation
	Video: how to be kind to yourself
	Further resources and links (e.g., videos, podcasts, and websites)
	to self-compassion, mindfulness, and stress management
Week 4:	Communication skills and tips for talking with health
Communication	professionals, your employer and your family
	Preparing for difficult conversations
	Asking for and accepting help
	Compassion for worries
	Further resources and links (e.g., videos, podcasts, and websites)
	to Long COVID support groups
Week 5:	How does COVID affect our sleep?
Sleep and mindfulness	Tips for sleeping better
	Tips to aide relaxation
	Introduction to Mindfulness, meditation and relaxation
Week 6:	Keeping active with Long COVID
Move better, feel better	Post-exertional malaise
	Tips for getting active
	Eating well for physical and mental health

	Managing changes to taste and smell after COVID-19
Week 7: Happiness and strengths	 Long COVID and effects on mood Happiness and hope Identifying your character strengths Understanding how using your strengths can lead to a more fulfilling life Video: The science of character strengths Managing setbacks Tips for authentic happiness; managing setbacks and keeping going
Week 8: Moving forward with Hope	 Hopes and dreams Doing something for yourself Planning pleasant activities Keeping in touch with peers Review of the programme Feedback Staying hopeful

Control group: Those allocated to the wait-list control group will access the intervention after follow-up data collection. It will be made clear to them that their responses on the measures will not be shared in an identifiable format with anyone involved in the intervention delivery and that neither their responses nor their participation in the study have any bearing on their subsequent access to the intervention.

This study will collect data from the delivery of the intervention within the community. As such, there are no criteria for discontinuing or modifying the intervention.

To improve adherence to intervention protocols, participants will receive a £10 gift voucher as thanks on completion of the questionnaires.

Owing to the setting of the study, no restrictions will be placed on the use of additional interventions or access to other care for participants.

Outcomes

Primary outcomes: Positive mental wellbeing measured using the Warwick-Edinburgh Mental Wellbeing Scale (WEMWBS) [21], at baseline and 8 weeks later. Emotional wellbeing is impacted by Long COVID [3], and our patient-public involvement groups have highlighted a desire for this to be the primary outcome measure for our self-management intervention. The measure also correlates highly with measures of mental illbeing, i.e. depression and anxiety scales [22].

Secondary outcome measures:

- 1. Self-efficacy measured by the Self-Efficacy for Managing Chronic Disease 6 item scale (SEMCD6) [23].
- 2. Fatigue measured by the Fatigue Severity Scale (FSS) [24]

- 3. Loneliness measured by the UCLA Loneliness Scale, Version 3 (UCLA3) [25]
- 4. Depression measured by the Patient Health Questionnaire 9 item scale (PHQ9) [26]. This measure will demonstrate both potential improvements and adverse effects in relation to clinical norms.
- 5. Anxiety measured by the Generalised Anxiety Disorder 7 item scale (GAD7) [27]. This measure will demonstrate both potential improvements and adverse effects in relation to clinical norms.
- 6. Long COVID symptoms reported via the COVID-19 Yorkshire Rehabilitation Screening Tool (C19-YRS) [28].

All measured at baseline and 8 weeks later.

Mean scores will be calculated for all outcomes. Classification into "caseness" for the depression and anxiety measures will be conducted, using established norms. This will allow investigation of the proportion of people moving between caseness and non-caseness (or vice versa).

Participant timeline

Participants who have already signed-up to the Hope Programme for Long COVID will be contacted by email to invite them to take part in the study. A link will allow them to view the information sheet, email address to contact with any questions, and complete the consent form. It will be made clear that their participation in the study is an entirely voluntary additional element that will not interfere with their ability to access the intervention. If consenting, participants will receive an email link to take them to the baseline measures to complete online, one week before the intervention starts The participants will then either have access to the intervention for 8 weeks, or be placed on the waiting list. Participants living outside of CWR area knew they were on the waiting list when they completed the baseline measures. At the end of the 8 week period, all participants will be emailed a link to complete post-intervention measures - collected within the two weeks following the end of the intervention.

Sample size

This was a pragmatic trial design. Approximately 50-60 participants from CWR area who sign up for the Hope Programme intervention, being run by H4C in January 2022, will constitute the intervention group. Our experience of running digital interventions has shown that optimum group size for social interaction and peer support is approximately 50-60. Participants from outside of the CWR area will be offered a place on another Hope Programme being run in March 2022. These participants will constitute the control group

Recruitment

Participants will be recruited via community groups and partners, social media, flyers placed in libraries, GP surgeries, long COVID clinics and through community events. Participants enrolled in the intervention will then be invited to take part in the study. This will not be a condition of their continued access to the intervention, rather explained that this is an option in addition. The delivery of this intervention in the community plans to recruit 100-120 participants.

Methods: Assignment of interventions

Allocation to the intervention or wait-list condition will be on a first-come, first-served basis. This is as our study takes place in the context of the real-life delivery of the intervention in the community. As such, there is no sequence generation. Allocation will not be concealed and no blinding will be used. All data will be collected using online questionnaires, without interaction with a researcher.

Methods: Data collection, management and analysis Data collection methods

Data will be collected at baseline and follow-up at the end of the intervention. All participants enrolled in the study will receive links to online questionnaires to complete, regardless of their engagement with the intervention platform. In addition to the measures listed as outcomes, basic demographic information will be collected (age, gender), and basic information about the impact of Long COVID on life (reduction in working hours). Long COVID symptoms will be assessed using the Covid-19 Yorkshire Rehabilitation Scale (C19-YRS) [28]. If participants do not complete their questionnaires within 7-14 days, they will be sent 3 reminders.

Data management

Data will be collected using Qualtrics, an online survey tool. No data entry will then occur by the research team, as everything will be electronically completed by participants. All completed data will be downloaded into SPSS.

Statistical methods

Descriptive statistics will summarise the characteristics of the participants and their movement through the study. Baseline characteristics and follow-up scores will be summarised.

An intention to treat analysis will take place, using multiple imputation to handle missing data.

A per-protocol (PP) analysis will also to include only those participants who completed all study questionnaires and attended at least 4 sessions of the intervention (in the intervention group), therefore are said to have "completed" the intervention.

Both analyses will compare follow-up scores between the two groups, covarying for the baseline score.

Methods: Monitoring

There are no data monitoring plans. We will be collecting data on an intervention occurring in real-life. The outcomes measures will allow us to examine harms in relation to changes in scores that indicate e.g. worsened depression, anxiety, or mental wellbeing. No interim analysis will be conducted. The intervention will be delivered on a digital platform. This is monitored by trained, lay facilitators. Any evidence of adverse events reported in participants' comments or interactions with the intervention will be shared with the researchers.

Ethics and dissemination

Research ethics approval

Approved 22/12/2021, Coventry University Research Ethics Committee ([name]; [contact]), ref: P106036.

Protocol amendments

The study examines the delivery of an intervention in real-life, as such we anticipate no changes to the intervention nor data collection schedule. Changes to the protocol will be recorded and reflected in the reporting of the results.

Consent or assent

Informed consent will be captured digitally: participants will be sent a link to the information sheet, details of who to contact with any questions, and then the digital consent form.

Confidentiality

Limited personal information is collected. Data will not be shared beyond the research team.

Declarations of interests

AT is the co-inventor of the HOPE Program and founder of Hope For The Community (H4C). GM and AL are the CEO and COO, respectively, of H4C.

Access to data

The research team will have access to the data set. There are no contractual requirements for sharing the data in relation to our funding. Interested researchers can contact the researchers to request access to the data.

Ancillary and post-trial care

This study examines an intervention delivered in real-life. The facilitators routinely provide signposting information for people who may require additional resources, for example signposting people for further mental health support.

Dissemination policy

The trial results will be shared with participants via the company delivering the intervention, using their website and email. We plan to publish results in academic publications. We do not intend to use professional writers.

References

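### Illness duration is neither restricted nor a named baseline item, so a difference in illness stage between the non-randomised groups would be neither described nor adjusted for

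*Protocol*

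**What the plan says.** **Who may enter.** Protocol, Eligibility: "Participants will be eligible if they are aged 18 years or older and self-defining as living with Long COVID". Nothing is verified: "self-report will be taken as evidence of person living with Long COVID". No minimum or maximum time since infection or onset is given.

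**What is recorded.** Protocol, Data collection methods, adds to the outcome measures: "basic demographic information will be collected (age, gender), and basic information about the impact of Long COVID on life (reduction in working hours". Symptoms are assessed with the C19-YRS, which is described only as a symptom measure. Time since infection or onset is not named there or elsewhere.

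**How groups are formed.** Protocol, Trial Design: "Randomisation to intervention or control group will not be conducted". That section and Methods: Assignment of interventions fill places in order of sign-up. Sample size instead makes residents of the local (CWR) area the intervention group and people from outside it the control group.

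**How groups are compared.** Under Participant timeline, the wait-list group is followed over the same interval: "At the end of the 8 week period, all participants will be emailed a link to complete post-intervention measures". Under Statistical methods, the intention-to-treat and per-protocol analyses both "compare follow-up scores between the two groups, covarying for the baseline score". No other covariate is stated.

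**The concern.** Someone a few weeks past infection and someone ill for 18 months can both enter with the same WEMWBS score. Their expected course over the next two months without any programme may differ. Adjusting for the baseline score equates the starting level, not the expected trajectory.

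In a randomised trial, illness duration would balance in expectation. Here, neither allocation route balances it. Recruitment runs through GP surgeries, Long COVID clinics, libraries, community events and social media, so local and distant participants may arrive through different channels and at different stages of illness. The protocol gives no evidence that they do, or in which direction.

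If the groups do differ, part of the contrast in WEMWBS, fatigue, PHQ9, GAD7 and the other outcomes would reflect illness stage rather than the programme. It could mimic a benefit or hide one. Under the plan as written, a reader of the results could not tell, because duration would not appear in the baseline table. Nor can an analysis plan adjust for a variable that was not collected.

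**Working it through.** The protocol gives no power, SD, effect size or recovery figure, so there is no stated number to reproduce. The calculations below only illustrate size.

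**1. Form of the bias.** Let g be the extra 8-week natural gain of recent-onset participants, and d the difference between groups in the share of such participants. If baseline adjustment absorbs none of it,

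bias = d × g.

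If d = 0, the bias is 0 however large natural recovery is. The problem is imbalance, not recovery as such.

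**2. Illustrative size.** Assumed, not from the documents: d from 0.10 to 0.30 and g from 3 to 8 WEMWBS points.

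- Low end: 0.10 × 3 = 0.3 points
- Midpoint: 0.20 × 5.5 = 1.1 points
- High end: 0.30 × 8 = 2.4 points

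**3. Comparison with the standard error.** Sample size plans 50–60 in the intervention group, and Recruitment plans 100–120 in all, which implies 50–60 per group. The background reports 60% retention in the pre-post study: 0.6 × 50 = 30 and 0.6 × 60 = 36 analysed per group. Assumed: SD 10, pre-post correlation 0.7.

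SE = 10 × √(1 − 0.7²) × √(2/n)

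- n = 30: 7.14 × 0.258 = 1.84
- n = 36: 7.14 × 0.236 = 1.68

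The midpoint bias is 1.1/1.84 = 0.60 to 1.1/1.68 = 0.65 of an SE. The high end is 2.4/1.84 = 1.30 to 2.4/1.68 = 1.43. To pass one SE at d = 0.30, g must exceed 1.68/0.30 = 5.6 to 1.84/0.30 = 6.1 points. At g = 8, d must exceed 1.68/8 = 0.21 to 1.84/8 = 0.23.

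**4. Effect on the false-positive rate.** Here the programme has no effect and the test is a two-sided 5% normal test with SE = SD × √(2/n). Assumed: g = 2, 4 or 6 points and residual SD 7–9.

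| d | Bias (points) | Rate, n = 55 per group | Rate, n = 30 per group |
|---|---|---|---|
| 0 | 0 | 5.0% | 5.0% |
| 0.1 | 0.2–0.6 | 5.2–7.3% | 5.1–6.3% |
| 0.2 | 0.4–1.2 | 5.6–14.6% | 5.3–10.2% |
| 0.3 | 0.6–1.8 | 6.4–27.1% | 5.8–16.9% |

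The rates are higher with 55 than with 30 per group: a larger sample shrinks the SE and leaves the bias untouched.

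**The case against.** **The wait-list already deals with natural recovery.** Largely right. A reader might infer that recovery cannot be separated from the programme effect at all. The documents do not support that: both groups are measured over the same 8 weeks, so recovery common to both cancels. For the same reason, the lack of a minimum illness duration is not in itself the defect. What stands is differential recovery, if illness stage differs between groups.

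**No mechanism for imbalance is shown.** True. The protocol gives no reason why residence or sign-up order should track duration. Duration is one possible confounder in an openly non-randomised study, and the root problem is non-random allocation with adjustment for the baseline score alone. That argues for modest weight. It does not argue against recording a plausible prognostic factor that costs one question.

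**The size is assumed throughout.** Also true. Imbalance, extra gain, SD and correlation have no source in the documents, and only the upper part of the range passes one SE. Baseline WEMWBS and C19-YRS severity may also carry some of the information in duration, although only the baseline score of each outcome is a stated covariate.

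**Onset may already be recorded, or could be asked later.** Neither the online form nor the C19-YRS items are shown, so the protocol establishes only that onset is not named. A reader might also infer that the imbalance could never be checked afterwards. That goes too far: onset is a fixed past date and participants are reachable by email, although non-responders would be missed.

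**Conclusion.** The point holds in a limited form. Illness duration is unrestricted, not named for collection and not in the stated adjustment, while allocation is non-random. An imbalance in illness stage would therefore be neither described nor adjusted for, and could bias the primary and secondary contrasts in either direction.

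The documents cannot quantify this. The illustrative 0.3–2.4 points, against an SE of 1.68–1.84, rests on assumed imbalance, recovery, SD and correlation, and on baseline adjustment absorbing none of the difference. With balanced duration the bias is nil. This is a worthwhile, inexpensive improvement, not evidence that the comparison is biased.

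**What to change.** Add one self-report item to the online questionnaire in both groups: month and year of the infection or symptom onset that led to Long COVID. If the form or the C19-YRS already records this, use it and say so. Report duration by group with the baseline characteristics, and include it as a covariate beside the baseline score in both analyses. Entry by self-report stays as it is.

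Baseline may already have closed: the intervention course is dated January 2022, while the reference list cites sources accessed in August 2022. In that case, ask the item at follow-up or by email. That adds the work of re-contact and leaves gaps for non-responders.

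Otherwise the cost is one question, some recall error, some missing values and one degree of freedom. Measuring duration deals with this confounder only; the comparison remains non-randomised.

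### In a non-randomised comparison split by area of residence, no socio-economic item is collected, so a social imbalance between the groups can be neither described nor adjusted for

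*Protocol*

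**What the plan says.** **Who is in each group.** The protocol's Sample size section describes the intervention group as "Approximately 50-60 participants from CWR area who sign up for the Hope Programme intervention". For the rest, "Participants from outside of the CWR area will be offered a place on another Hope Programme being run in March 2022", and it names these people as the control group. Trial Design and Methods: Assignment of interventions instead describe allocation in order of sign-up until places run out. Study setting adds that "Residents of Coventry, Warwickshire and Rugby will be given priority access to the Hope Programme".

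**How people are found.** Under Recruitment: "Participants will be recruited via community groups and partners, social media, flyers placed in libraries, GP surgeries, long COVID clinics and through community events".

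**What is recorded.** Under Data collection methods, on top of the outcome scales, "basic demographic information will be collected (age, gender), and basic information about the impact of Long COVID on life (reduction in working hours"). The same section says "Long COVID symptoms will be assessed using the Covid-19 Yorkshire Rehabilitation Scale (C19-YRS"). Confidentiality states "Limited personal information is collected". Education, employment status, ethnic group, deprivation and recruitment route are named nowhere.

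**What is adjusted for.** Statistical methods compares follow-up scores between the groups with the baseline score as the only covariate, in both the intention-to-treat and per-protocol analyses. Missing data are to be handled by multiple imputation.

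**Background.** The introduction remarks that "Digital interventions must be carefully reviewed to ensure they do not deepen health inequalities". The Objectives section does not take this up.

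**The concern.** Without randomisation, the comparison rests on how alike the two groups are and on what can be done about the ways in which they differ. Here the feature that separates them is where people live. If the split in Sample size is complete, residence coincides with treatment and cannot itself be adjusted for. Only person-level characteristics can then show whether the groups are socially alike, and none is collected.

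The baseline WEMWBS score does not fill this gap. It removes the part of a group difference already carried in that score. It does not remove a difference in how wellbeing would have moved over the 8 weeks. If social position affects that course and differs between the groups, its effect would be counted as a programme effect or would mask one.

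Missing data add to this. The introduction reports 60% retention in the earlier pre-post study of the programme. Multiple imputation is more credible when predictors of dropout are measured, and social predictors would not be.

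The list of survey items is a data-collection decision fixed in the protocol. It is not a detail that can be left to an analysis plan.

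**Working it through.** The protocol gives no effect size, standard deviation, power or error rate, so there is no stated figure to reproduce. The check is one of text, followed by an illustration on assumed inputs.

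**Text check**

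1. The list of background items is closed: two demographic items and one illness-impact item, with no wording to suggest examples.
2. Reduction in working hours records the effect of the illness. It is at most a weak proxy for social position, and is hard to read without knowing whether the person worked before COVID.
3. The allocation statements disagree (area in Sample size, order of sign-up in Assignment of interventions) and must be reconciled. Because Study setting gives CWR residents priority, area is tied to group on either reading.
4. The model uses the baseline score only, so even age, gender and working hours are collected without being named as covariates.

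**Illustration A, in WEMWBS points**

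Assumptions, none from the protocol: SD 10; baseline to follow-up correlation 0.7; an unmeasured two-level factor whose prevalence differs by 20 percentage points between groups; an effect of 3 to 6 points left after baseline adjustment. Group sizes: 55, the middle of the stated 50 to 60 and assumed equal in the control group; and 33, which is 60% of 55.

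- Bias = prevalence difference × remaining effect: 0.20 × 3 = 0.6 and 0.20 × 6 = 1.2 points.
- Residual SD = 10 × √(1 − 0.49) = 7.14.
- SE = 7.14 × √(2/n): 1.36 at n = 55 and 1.76 at n = 33.
- Bias in SE units: from 0.6/1.76 = 0.34 to 1.2/1.36 = 0.88.
- Two-sided error at a nominal 5%, from 1 − Φ(1.96 − b) + Φ(−1.96 − b), where b is the bias in SE units: about 6% at 0.34 and 14% at 0.88.

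The assumed effect is generous: 3 to 6 points is 3/7.14 = 0.42 to 6/7.14 = 0.84 residual SD for a single factor.

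**Illustration B, in SD units and with a wider grid**

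Assumptions: imbalance of 10 to 30 percentage points; remaining effect of 0.2 to 0.5 SD; 50 to 60 per group; SE = √(2/n), that is 0.200 at n = 50 and 0.183 at n = 60.

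| Imbalance × effect | Bias (SD) | Error at 50 per group | Error at 60 per group |
|---|---|---|---|
| 0.1 × 0.2 | 0.02 | 5.1% | 5.1% |
| 0.2 × 0.3 | 0.06 | 6.0% | 6.3% |
| 0.3 × 0.5 | 0.15 | 11.7% | 13.0% |

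The result runs from negligible to more than double the nominal rate. Nothing in the document says where in that range the study lies.

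**The case against.** The strongest reply is that this asks for extra items and exposes no contradiction. The survey already carries seven scales for people with fatigue and brain fog, and the decision to hold little personal data looks deliberate. The bias is assumed, and in illustration A it stays below one standard error even with a generous effect. That stands as far as size goes. It does not answer the structural point that, in a non-randomised design, an uncollected variable can be neither shown nor used.

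Several stronger readings are tempting, and the document does not support them:

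- **That the groups' comparability would be invisible.** It would not. Wellbeing, self-efficacy, fatigue, loneliness, depression, anxiety, Long COVID symptoms, age, gender and working hours are all available at baseline. Only social comparability is hidden.
- **That the protocol fails one of its own aims on inequality.** The remark is background about digital interventions in general. The objectives contain no equity question, and age and gender allow a limited look.
- **That the survey should have measured uptake across social groups.** Only people who signed up and consented complete it, so no added item could do that.
- **That the groups divide cleanly by area.** Sample size says so, but the order-of-sign-up statements would let late CWR applicants fall into the wait-list.
- **That recruitment routes differ by area.** This is plausible, but the protocol links no route to an area or a group.

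Timing is also a fair objection. The course is dated January 2022, some text is in the past tense, and sources were accessed as late as August 2022. Baseline collection may therefore be over.

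**Conclusion.** The point holds in this limited form. Area of residence is tied to group. The collected background items contain no direct measure of social position, and the planned model uses none of them. A socio-economic imbalance can therefore be neither described nor adjusted for, and an analysis plan written later cannot change that.

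The size of any bias is unknown. The ranges shown (0.6 to 1.2 points, or 0.02 to 0.15 SD; error rates of about 5% to 14%) depend wholly on assumed imbalances, effects, SD and correlation, and on equal group sizes that the protocol does not state. They show that the issue could matter. They do not show that the result is biased.

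This is a worthwhile and inexpensive improvement and does not invalidate the study. Measured items would reduce confounding but would not remove it.

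**What to change.** 1. Add four banded tick-box items to the Qualtrics survey: highest education, employment status before COVID, ethnic group, and how the person heard about the programme.
2. If baseline is complete, ask them at follow-up, since the answers are largely fixed. They would then be missing for those who do not respond, so they would help the adjustment more than the imputation. If they can no longer be asked, state the gap as a limitation.
3. Show all four by group in the baseline table.
4. Pre-specify a small covariate set for the intention-to-treat comparison and the imputation model: baseline score, age, gender, education and employment. Age and gender cost nothing extra to collect.
5. Keep any table of retention, or of completing at least 4 sessions, by social group descriptive. With about 50 to 60 treated people some cells will be very small.
6. Reconcile the allocation statements in Sample size, Trial Design and Assignment of interventions, so that readers know how area relates to group.

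Cost: about one minute of survey time, slightly more personal data, an ethics amendment, and a few degrees of freedom. With three bands each for education and employment, one term for age and one for gender, that is 2 + 2 + 1 + 1 = 6, which is affordable with 100 to 120 participants but a reason to keep the set small. If baseline has closed, there is also the effort of asking retrospectively.
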